#### **5.4. Prior Anti-cancer Therapy**

Prior anti-cancer therapies will be summarized based on the Safety Analysis Set.

Number of subjects who received prior anti-cancer therapies and the number of prior regimens that each subject received will be summarized by cohort and overall using descriptive statistics. The regimens and prior therapies that the subjects received will be summarized by cohort and overall.

Number of subjects who received prior radiotherapies and the number of prior radiotherapies that each subject received will be summarized by cohort and overall.

Number of subjects who received prior surgeries or procedures and the prior surgeries or procedures that the subjects received will be summarized by cohort and overall.

By-subject listings will be provided for prior and post study anti-cancer therapies, radiotherapies, and surgery or procedures by subject ID number in ascending order.

## 6. EFFICACY ANALYSES

### 6.1. Exploratory Efficacy Endpoints

#### 6.1.1. Definition of the Exploratory Efficacy Endpoints

**CCI** [REDACTED]  
[REDACTED]

[REDACTED]  
[REDACTED]

[REDACTED]  
[REDACTED]

[REDACTED]  
[REDACTED]

**CCI** [REDACTED]  
[REDACTED]

[REDACTED]  
[REDACTED]

[REDACTED]  
[REDACTED]

**CCI**

[Redacted]

**6.1.2. Analysis of the Exploratory Efficacy Endpoints**

**CCI**  
[Redacted]

[Redacted]

**6.2. Change from Protocol-Specified Efficacy Analyses**

For this synoptic CSR, the exploratory efficacy endpoints will not be derived or summarized.

## **7. SAFETY ANALYSES**

### **7.1. Adverse Events and Deaths**

#### **7.1.1. Adverse Event Dictionary**

Clinical and laboratory adverse events (AEs) will be coded using the current version of MedDRA. System organ class (SOC), high-level group term (HLGT), high-level term (HLT), preferred term (PT), and lower-level term (LLT) will be provided in the AE dataset.

#### **7.1.2. Adverse Event Severity**

Adverse events are graded by the investigator as Grade 1, 2, 3, 4, or 5 according to CTCAE Version 4.03. The severity grade of events for which the investigator did not record severity will be categorized as “missing” for tabular summaries and data listings. The missing category will be listed last in summary presentation.

#### **7.1.3. Relationship of Adverse Events to Study Drug**

Related AEs are those for which the investigator selected “Related” on the AE CRF to the question of “Related to Study Treatment.” Relatedness will always default to the investigator’s choice, not that of the medical monitor. Events for which the investigator did not record relationship to study drug will be considered related to study drug for summary purposes. However, by-subject data listings will show the relationship as missing.

#### **7.1.4. Serious Adverse Events**

Serious adverse events (SAEs) will be identified and captured as SAEs if the AEs met the definitions of SAEs that were specified in the study protocol. SAEs captured and stored in the clinical database will be reconciled with the SAE database from the Gilead Pharmacovigilance and Epidemiology Department before data finalization.

#### **7.1.5. Treatment-Emergent Adverse Events**

##### **7.1.5.1. Definition of Treatment-Emergent Adverse Events**

Treatment-emergent adverse events (TEAEs) are defined as 1 or both of the following:

- Any AEs with an onset date on or after the date that ADX and if applicable, nivolumab was first administered and no later than 30 days after permanent discontinuation of ADX, or if applicable, 5 months after permanent discontinuation of nivolumab (whichever is later).
- Any AEs leading to premature discontinuation of ADX and if applicable, nivolumab.

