Finally, {[Kang 2017](#)} demonstrated improved efficacy of nivolumab monotherapy compared to placebo as salvage treatment for patients who have received at least 2 lines of treatment for advanced gastric/gastroesophageal junction (GEJ) adenocarcinoma. The median OS was 5.32 months in the nivolumab arm versus 4.14 months in the placebo arm (HR, 0.63; 95%, CI, 0.50-0.78; p,0.0001) while the median PFS was 1.61 months versus 1.45 months for the nivolumab and placebo arms, respectively (HR, 0.60; 95% CI, 0.49-0.75; p,0.0001).

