6.10.3. Long Term Follow-Up

Long term follow-up (LTFU) for OS begins after the EOS visit, or the last visit on study if EOS does not occur. Subjects will be contacted via phone call every 3 months for determination of long term survival status and record of any other anti-cancer therapy, cancer-related surgery for up to 5 years after the EOS visit.

Subjects who are not deceased by the time Gilead has made the determination the study will be ended will receive a final follow-up phone call to assess survival status and communicate the sponsor's decision.

The investigator will make every effort to contact the subject or a close relative or caretaker by phone to collect survival information. The investigator should show due diligence by documenting in the source documents steps taken to contact the subject (ie, dates of phone calls, registered letters, etc).

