7.3.1. Adverse Events

Following initiation of study medication, all AEs, regardless of cause or relationship, until 30 days after last administration of andecaliximab and 5 months post-treatment of nivolumab, must be reported to the eCRF database as instructed.

All AEs should be followed up until resolution or until the adverse event is stable, if possible.

Gilead Sciences may request that certain AEs be followed beyond the protocol defined follow-up period.

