8.3. Data Handling Conventions

By-subject listings will be created for important variables from each eCRF module. Summary tables for continuous variables will contain the following statistics: N (number in population), n (number with data), mean, standard deviation, 90% confidence intervals (CIs) on the mean, median, minimum, and maximum. Summary tables for categorical variables will include: N, n,

percentage, and 90% CIs on the percentage. Unless otherwise indicated, 90% CIs for binary variables will be calculated using the binomial distribution (exact method) and will be 2 sided. Data will be described and summarized by dose level/cohort, analysis set, and time point. As appropriate, changes from baseline to each subsequent time point will be described and summarized. Similarly, as appropriate, the best change from baseline during the study will also be described and summarized. Graphical techniques (eg, waterfall plots, Kaplan-Meier (KM) curves, line plots) may be used when such methods are appropriate and informative.

The baseline value used in each analysis will be the last (most recent) pretreatment value. Data from all sites will be pooled for all analyses. Analyses will be based upon the observed data unless methods for handling missing data are specified. If there is a significant degree of non-normality, analyses may be performed on log-transformed data or nonparametric tests may be applied, as appropriate.

The following censoring conventions will be applied to tumor control endpoints:

- PFS: Data from surviving, non-progressing subjects will be censored at the earliest of the time of initiation of antitumor treatment other than the study treatment or the last time that lack of definitive progression was objectively documented. Data from subjects who have disease progression or die after ≥ 2 consecutive missing tumor assessments will be censored at the last time prior to the missing assessments that lack of definitive disease progression was objectively documented.
- OS: Data from surviving subjects will be censored at the last time that the subject was known to be alive.

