#### **4.2.2. Exposure to Chemotherapy**

Exposure to chemotherapy agents, including cisplatin, oxaliplatin and nivolumab, will be listed. Duration of exposure and the total number of doses that each subject received during the study will be summarized for each agent in a similar manner as for ADX. Chemotherapy received prior to study enrollment and after the start of other anti-cancer therapy will not be included in the summary.

S-1 was administered orally twice daily. A by-subject listing of S-1 administration will be provided by subject ID number (in ascending order), including dose per administration, dose frequency, start and stop date, and reason for dose interruption or modification (if applicable).

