#### **7.2.2.1. Treatment-Emergent Laboratory Abnormalities**

Treatment-emergent laboratory abnormalities are defined as values that increase at least 1 toxicity grade from baseline at any post-baseline time point, up to 30 days after the last dose of ADX, or if applicable, 5 months after the last dose of nivolumab (whichever is later). If the relevant baseline laboratory value is missing, then any abnormality of at least Grade 1 observed within the time frame specified above will be considered treatment emergent.

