### **7.6. Other Safety Measures**

All post treatment anti-cancer therapies (other than those allowed per-protocol) will be provided in a by-subject listing sorted by subject ID number and administration date in chronological order. A summary of post treatment anti-cancer therapies will not be provided.

A data listing will be provided for the results of all pregnancy tests conducted in the study.

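### Cohort 4 any-cause adverse-event and laboratory tables run to 5 months after nivolumab with no cut-off or flag at the next anti-cancer therapy, so next-line events are mixed in

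*SAP*

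**What the plan says.** **The window.** SAP 7.1.5.1 accepts events with onset "no later than 30 days after permanent discontinuation of ADX, or if applicable, 5 months after permanent discontinuation of nivolumab (whichever is later"). SAP 7.1.5.2 applies the same end to incomplete onset dates. SAP 7.2.2.1 carries treatment-emergent laboratory abnormalities to "5 months after the last dose of nivolumab (whichever is later"), and SAP 7.2.2.2 builds the laboratory denominator on that period. None of these mentions later therapy.

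**The data.** Protocol 7.3.1 requires sites to report "all AEs, regardless of cause or relationship, until 30 days after last administration of andecaliximab and 5 months post-treatment of nivolumab". Protocol 8.6 summarises safety over the same period. Protocol 8.6.2, however, ends the treatment-emergent period 30 days after the last andecaliximab dose. SAP 7.7 does not list this as a change; it mentions only that continuous safety data will not be summarised.

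**Later therapy.** Protocol 5.4 bars non-study anticancer treatment during the trial, but progression can end participation (protocol 3.7). Long-term follow-up then includes a "record of any other anti-cancer therapy, cancer-related surgery for up to 5 years after the EOS visit". SAP 7.6 lists these treatments by subject and date, and adds: "A summary of post treatment anti-cancer therapies will not be provided".

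**The tables.** SAP 7.1.6.1 tabulates any-cause events (all, Grade 3 or higher, serious, fatal) by cohort. Separate tables cover events and serious events related to each drug. Under SAP 7.1.3, an event with no recorded causality counts as related.

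**The concern.** Safety is the primary endpoint (protocol 8.1.2), and for Cohort 4 the question is what andecaliximab with nivolumab does to patients. A subject may progress, leave the study, start another regimen and develop Grade 4 neutropenia inside the 5 months. Once reported, that event sits in the any-cause and Grade 3 or higher rows beside events that arose on study treatment, and the table does not show which is which. In a cohort of at most 10, one or two such subjects visibly change a row.

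The start of other therapy is already a working boundary in two other places. Under SAP 4.2.2, chemotherapy given "after the start of other anti-cancer therapy will not be included in the summary". Under protocol 8.3, PFS and duration of response are censored at the "earliest of the time of initiation of antitumor treatment other than the study treatment" or the last documented absence of progression. Those rules serve exposure and efficacy, so they do not show that safety was meant to be cut there. They do show that the date is one the analysis already expects to handle.

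**Working it through.** The plan gives no figure on this point, so there is none to reproduce. The check is a comparison of the rules, followed by window arithmetic.

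**1. Where next-line events can enter (Cohort 4)**

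| Display | Stops at new therapy? | Uses causality? | Reach |
|---|---|---|---|
| Any-cause TEAE, Grade 3 or higher, SAE, fatal (SAP 7.1.6.1) | No | No | Any reported event in the window |
| Related to andecaliximab; related to nivolumab (SAP 7.1.6.1) | No | Yes | Only events judged related or left blank |
| Laboratory abnormalities (SAP 7.2.2.1, 7.2.2.2) | No | No | After EOS: 30-day and 5-month visits, plus unscheduled or local results |
| ECG (SAP 7.5) | No | No | Negligible: none is scheduled after EOS (protocol 6.12.6) |

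SAP 7.1.6.1 lists a Grade 3 or higher table for andecaliximab-related events but none for nivolumab-related events. The nivolumab-related table is, however, split by maximum severity. On laboratory data, SAP 3.8.2 and 7.2.2 let unscheduled and local results count toward the worst grade.

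**2. Length of the window**

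- 5 months × 30.4375 days = 152 days after the last nivolumab dose.
- Against the 30 days of protocol 8.6.2: 152 − 30 = 122 extra days, and 152/30 = 5.1 times as long.

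**3. Overlap with later therapy (assumed start)**

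The documents do not give the time from last nivolumab dose to next therapy. For a start on day d, overlap = 152 − d; with a 30-day window it is max(0, 30 − d).

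| d (assumed) | Days of 152 after start | Share | Days with a 30-day window |
|---|---|---|---|
| 14 | 138 | 91% | 16 |
| 28 | 124 | 82% | 2 |
| 42 | 110 | 72% | 0 |
| 56 | 96 | 63% | 0 |
| 84 | 68 | 45% | 0 |

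These shares apply only to a subject who starts a next therapy and is followed to the end of the window.

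**4. Effect on a row**

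One subject shifts a row by 1/n. With the full 10 subjects (SAP 1.3) that is 10 percentage points. It is more if fewer enrol, or if fewer have a post-baseline laboratory value: 1/8 = 12.5 points.

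**5. Illustration only**

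Assume that 30–70% of 10 subjects start a next therapy inside the window, and that 20–60% of those have a Grade 3 or higher event on it, independently between subjects.

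- Expected subjects with such an event: 10 × 0.3 × 0.2 = 0.6 to 10 × 0.7 × 0.6 = 4.2.
- Chance of at least one: 1 − 0.94^10 = 46% to 1 − 0.58^10 = over 99%.

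Both inputs are assumptions. A subject who already had a Grade 3 or higher event on study treatment would not raise the overall count again.

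**6. A figure that does not measure this**

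Protocol 1.1.1 reports for a nivolumab trial that "the median PFS was 1.61 months versus 1.45 months for the nivolumab and placebo arms". Taking 1.61 months (49 days) as time on treatment, 152/(49 + 152) = 76% of the event window lies after the last dose. That is time off study treatment, not time on another therapy.

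**The case against.** The best defence is that an any-cause table records timing and makes no claim about cause. Attribution has its own tables, so neutropenia on salvage chemotherapy that is marked unrelated never reaches them. Events and later therapies are both listed by subject, and with at most 10 subjects a reader can match them by hand. Keeping every event to 5 months is a sound, inclusive choice in a Phase 1b safety study, since late immune-mediated events would otherwise be missed. No formal testing is planned (SAP 3.5), and the window agrees with protocol 8.6.

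Most of this stands. The length of the window is not the fault, and the related-event tables are a real safeguard. Three gaps remain: blank causality defaults to related, laboratory tables have no attribution, and the any-cause tables carry no marker that would spare the reader the hand matching.

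Several stronger readings are tempting but unsupported:

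- That next-line toxicity is attributed to andecaliximab plus nivolumab. The any-cause tables attribute nothing.
- That about three quarters of the window is contaminated. The 76% is time after the last dose. It also borrows a PFS from patients with at least 2 prior lines, whereas Cohort 4 requires at least 1 and may be treated past first radiologic progression (protocol 6.12.9.2).
- That the missing cut-off makes Cohort 4 look worse than Cohorts 1–3. Those cohorts have no cut-off either. The windows differ in length whether or not later therapy is given, and no between-cohort test is planned.
- That an isolated cytopenia 3 months after nivolumab must enter the laboratory tables. It falls between the two scheduled visits and enters only through an unscheduled or local result.

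**Conclusion.** The point holds with limited scope. In Cohort 4, events arising on the next line of therapy are mixed into the any-cause safety tables, and less often into the laboratory tables, with no cut-off or flag. The related-event tables contain the problem where causality is recorded as unrelated. ECG summaries are effectively untouched.

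The direction is upward: next-line events can only add to the any-cause counts. The size is unknown, because neither document gives the rate or timing of subsequent therapy. The firm statement is 10 percentage points or more per affected subject per row, given at most 10 subjects and no earlier event of that type in the subject. This is a cheap improvement to interpretation and does not invalidate the safety analysis. The differing treatment-emergent definitions in protocol 8.6.2 and SAP 7.1.5.1 need reconciling in any case.

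**What to change.** 1. Keep the full 5-month Cohort 4 tables unchanged.
2. Add, for Cohort 4, a second display of all TEAEs, Grade 3 or higher TEAEs, SAEs and treatment-emergent laboratory abnormalities. End it at the earlier of the current window end and the day before the first subsequent anti-cancer therapy. Cut the laboratory denominator in SAP 7.2.2.2 at the same date so that numerator and denominator match.
3. In the adverse-event listing, flag any event with onset on or after the start of later therapy.
4. State a rule for partial start dates of later therapy. One option is to treat an event as later-onset only when the known date parts make this certain. Query missing dates before the database is finalised: later therapy is recorded at 3-monthly calls, and the 30-day visit asks for it only when a subject left without progression (protocol 6.10.1).
5. Reconcile SAP 7.1.5.1 with protocol 8.6.2 and record the departure in SAP 7.7. Check protocol 8.6.3 at the same time: it sends laboratory abnormalities from 30 days after treatment discontinuation to a listing.

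**Cost.** SAP wording, a small set of extra Cohort 4 tables in a synoptic report, and some date cleaning. Later therapies are already collected and listed. Late events that begin after new therapy will appear only in the full-window tables and the listing, so both displays must be shown together.

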#### 7.1.5.2. Incomplete Dates

If the onset date of the AE is incomplete and the AE stop date is not prior to the first dosing date of study drug, then the month and year (or year alone if month is not recorded) of onset determine whether an AE is treatment emergent. The event is considered treatment emergent if both of the following 2 criteria are met:

- The AE onset is the same as or after the month and year (or year) of the first dosing date of study drug, and
- The AE onset date is the same as or before the month and year (or year) of the date corresponding to 30 days after the date of the last dose of ADX, or if applicable, 5 months after the last dose of nivolumab (whichever is later).

An AE with completely missing onset and stop dates, or with the onset date missing and a stop date later than the first dosing date of study drug, will be considered to be treatment emergent. In addition, an AE with the onset date missing and incomplete stop date with the same or later month and year (or year alone if month is not recorded) as the first dosing date of study drug will be considered treatment emergent.

#### 7.1.6. Summaries of Adverse Events and Deaths

Treatment-emergent AEs will be summarized based on the Safety Analysis Set.

##### 7.1.6.1. Summaries of AE Incidence by Severity

The number and percentage of subjects who experienced at least 1 TEAE will be provided and summarized by SOC, HLT (if applicable), PT, and cohort. For the AE categories described below, summaries will be provided by SOC, PT, maximum severity, and cohort:

- TEAEs
- TEAEs with Grade 3 or higher
- TEAEs related to ADX
- TEAEs related to S-1
- TEAEs related to oxaliplatin
- TEAEs related to cisplatin
- TEAEs related to nivolumab
- TEAEs related to ADX with Grade 3 or higher
- TE SAEs

- TE SAEs related to ADX
- TE SAEs related to S-1
- TE SAEs related to oxaliplatin
- TE SAEs related to cisplatin
- TE SAEs related to nivolumab
- TEAEs leading to premature discontinuation of ADX
- TEAEs leading to premature discontinuation of S-1
- TEAEs leading to premature discontinuation of oxaliplatin
- TEAEs leading to premature discontinuation of cisplatin
- TEAEs leading to premature discontinuation of nivolumab
- TEAEs leading to death (summarize by SOC and PT as all TEAEs leading to death will be Grade 5.)
- TEAEs leading to dose modification or temporary interruption of ADX
- TEAEs leading to dose modification or temporary interruption of S-1
- TEAEs leading to dose modification or temporary interruption of oxaliplatin
- TEAEs leading to dose modification or temporary interruption of cisplatin
- TEAEs leading to dose modification or temporary interruption of nivolumab

A brief, high-level summary of AEs described above will be provided by cohort and by the number and percentage of subjects who experienced the above AEs.

Multiple events will be counted only once per subject in each summary. Adverse events will be summarized and listed first in alphabetic order of SOC and HLT within each SOC (if applicable) and then by PT in descending order of total frequency within each SOC. For summaries by severity, the most severe severity will be used for those AEs that occurred more than once in a given subject during the study.

In addition to the above summary tables, all TEAEs, TEAEs of Grade 3 or higher, TE SAEs and TE ADX-related AEs will be summarized by PT only in descending order of total frequency.

In addition, data listings will be provided as follows:

- All AEs, indicating whether the event is treatment emergent
- All AEs with Grade 3 or higher
- All SAEs
- All AEs leading to death
- All AEs leading to premature discontinuation of any study drug (ADX, S-1, oxaliplatin, cisplatin and nivolumab)
- All AEs leading to dose modification or temporary interruption of any study drug (ADX, S-1, oxaliplatin, cisplatin and nivolumab)
- All AEs related to any study drug (ADX, S-1, oxaliplatin, cisplatin and nivolumab)
- All AEs with Grade 3 or higher related to ADX
- All deaths

#### 7.1.6.2. Summaries of Deaths

A summary (number and percentage of subjects) of deaths will be provided by cohort. The summary will include the following categories:

- All deaths
- Deaths within 30 days of the last dosing of ADX, or if applicable, 5 months after the last dose of nivolumab (whichever is later)
- Deaths beyond 30 days of the last dosing of ADX, or if applicable, 5 months after the last dose of nivolumab (whichever is later)

All death will be summarized by the cause of the death (AE, PD, or other reasons).

#### 7.1.7. Additional Analysis of Adverse Events

##### 7.1.7.1. Dose Limiting Toxicity

A listing of the DLT AEs will be provided.

A summary of DLTs will be presented by SOC and decreasing frequency of preferred term within SOC using the DLT Analysis Set for Cohort 1.

